• To evaluate the objective response rate per RECIST 1.1 as assessed by blinded independent central review for MK-7684A in combination with the background therapy of etoposide/platinum followed by MK-7684A compared to atezolizumab in combination with the background therapy of etoposide/platinum followed by atezolizumab.	• Objective response: complete response or partial response
• To evaluate duration of response per RECIST 1.1 as assessed by blinded independent central review for MK-7684A in combination with the background therapy of etoposide/platinum followed by MK-7684A compared to atezolizumab in combination with the background therapy of etoposide/platinum followed by atezolizumab.	• Duration of response: for participants with confirmed complete response or partial response, duration of response is defined as time from first documented evidence of complete response or partial response until disease progression or death due to any cause, whichever occurs first
• To evaluate the safety and tolerability of the investigational treatment combination based on proportion of adverse events.	 Adverse events Study intervention discontinuations due to adverse events

• To evaluate the mean change from baseline in global health status/quality of life, physical functioning, dyspnea, cough, and chest pain for MK-7684A in combination with the background therapy of etoposide/platinum followed by MK-7684A compared to atezolizumab in combination with the background therapy of etoposide/platinum followed by atezolizumab.	 Change from baseline in the following patient-reported outcomes scales/items: Global health status/quality of life score (EORTC QLQ-C30 items 29 and 30) Physical functioning score (EORTC QLQ-C30 items 1-5) Dyspnea score (EORTC QLQ-C30 item 8) Cough (EORTC QLQ-LC13 item 31) Chest pain (EORTC QLQ-LC13 item 40)

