9 STATISTICAL ANALYSIS PLAN

At implementation of Amendment 05, the below changes apply. The changes listed below supersede any protocol content/instructions from previous amendments.

- Participants with access to approved SOC (eg, immunotherapy, chemotherapy, targeted therapy) should be considered for discontinuation from the study. Those benefiting from atezolizumab, but unable to access it as SOC outside the study, may continue on study and receive treatment with atezolizumab until discontinuation criteria are met. The final required study visit will be the Safety Follow-up Visit.
- Participants who complete study treatment or otherwise meet EOT criteria will be discontinued from the study after the EOT visit and any required safety follow-up visit.
- There will be no follow up for survival status. Participants currently in imaging follow-up or survival follow-up are considered to have completed the study and therefore should obtain imaging and further oncological care as per local SOC. Standard safety reporting should, however, continue, as applicable.
- Participants remaining on study at the time of Amendment 05 should continue to be monitored in the study through the AE reporting period (Section 8.4).

Existing protocol content is retained for historical reference.

Protocol Amendment 04 implementation: based on recommendations of the eDMC following the interim efficacy/safety analysis (data cutoff 04-JUN-2024) which showed that the primary endpoint of overall survival met the pre-specified futility criteria, the study was unblinded, the experimental arm (Arm A: MK-7684A) will be discontinued and all ongoing participants on MK-7684A treatment will be offered the option to move to the comparator arm (Arm B: atezolizumab monotherapy) for the remainder of the study. The prespecified final analysis of the study described in the SAP will not be performed. Safety analysis will be performed at the end of the study. There will be no further analyses for efficacy and ePRO endpoints collected from participants after IA cutoff date.

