This section outlines the statistical analysis strategy and procedures for the study. If, after the study has begun, but prior to any unblinding/final database lock, changes are made to primary and/or key secondary hypotheses, or the statistical methods related to those hypotheses, then the protocol will be amended (consistent with ICH Guideline E9). Changes to exploratory or other nonconfirmatory analyses made after the protocol has been finalized, but prior to the conduct of any analysis, will be documented in a sSAP and referenced in the CSR for the study. Post hoc exploratory analyses will be clearly identified in the CSR. Other planned analyses (ie, those specific to the analysis of ePROs) will be documented in an sSAP.

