9.5.2 Safety Analysis Populations

Safety Analyses will be conducted in the All Participants as Treated (APaT) population, which consists of all randomized participants who received at least 1 dose of study intervention. Participants will be included in the treatment group corresponding to the study intervention they actually received for the analysis of safety data using the APaT population. This will be the treatment group to which they are randomized except for participants who take incorrect study intervention for the entire treatment period; such participants will be included in the treatment group corresponding to the study intervention actually received. Any participant who receives the incorrect study intervention for 1 cycle, but receives the correct treatment for all other cycles, will be analyzed according to the correct treatment group and a narrative will be provided for any events that occur during the cycle for which the participant is incorrectly dosed.

At least 1 laboratory or vital sign measurement obtained after at least 1 dose of study intervention is required for inclusion in the analysis of each specific parameter. To assess change from baseline, a baseline measurement is also required.

9.5.3 **PRO Analysis Populations**

The PRO analyses are based on the PRO Full Analysis Set (PRO FAS) Population, defined as all randomized participants who have at least one PRO assessment available for the specific endpoint and have received at least one dose of the study intervention. Participants will be analyzed in the treatment group to which they are randomized.

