9.6.2 Statistical Methods for Safety Analyses

Safety and tolerability will be assessed by clinical review of all relevant parameters, including AEs, laboratory tests, vital signs, and ECG measurements.

The analysis of safety results will follow a tiered approach (Table 14). The tiers differ with respect to the analyses that will be performed. Safety parameters or adverse experiences of special interest that are identified a priori constitute "Tier 1" safety endpoints that will be subject to inferential testing for statistical significance with p values and 95% confidence intervals provided for between-group comparisons. Other safety parameters will be considered Tier 2 or Tier 3 based on the observed proportions of participants with an event. Tier 2 parameters will be assessed via point estimates with 95% confidence intervals provided for between-group comparisons; only point estimates by treatment group are provided for Tier 3 safety parameters.

Tier 1 Events

Safety parameters or adverse events of special interest (AEOSI) that are identified a priori constitute "Tier 1" safety endpoints that will be subject to inferential testing for statistical

significance. AEOSI that are immune-mediated or potentially immune-mediated are well documented and will be evaluated separately; however, these events have been characterized consistently throughout the pembrolizumab clinical development program and determination of statistical significance is not expected to add value to the safety evaluation. Finally, the addition of MK-7684A to etoposide/platinum treatments included in the study is not anticipated to be associated with any new safety signals. Therefore, there are no Tier 1 events expected in this study.

Tier 2 Events

Tier 2 parameters will be assessed via point estimates with 95% CIs provided for differences in the proportion of participants with events using the Miettinen and Nurminen (M&N) method [Miettinen, O. and Nurminen, M. 1985], an unconditional, asymptotic method.

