Membership in Tier 2 requires that at least 10% of participants in any treatment group show the event; all other AEs and predefined limits of change will belong to Tier 3. The threshold of at least 10% of participants was chosen for Tier 2 events because the population enrolled in this study is in critical condition and usually experiences various AEs of similar types regardless of treatment; events reported less frequently than 10% of participants would obscure the assessment of the overall safety profile and add little to the interpretation of potentially meaningful treatment differences. In addition, Grade 3 to 5 AEs (\geq 5% of participants in 1 of the treatment groups) and SAEs (\geq 1% of participants in 1 of the treatment groups) will be considered Tier 2 endpoints. Because many 95% CIs may be provided without adjustment for multiplicity, the CIs should be regarded as a helpful descriptive measure to be used in safety review, not as a formal method for assessing the statistical significance of the between-group differences.

Tier 3 Events

Safety endpoints that are not Tier 1 or 2 events are considered Tier 3 events. The broad AE categories consisting of the proportion of participants with any AE, a drug-related AE, a serious AE, an AE that is both drug-related and serious, a Grade 3-5 AE, a drug-related Grade 3-5 AE, and discontinuation due to an AE will be considered Tier 3 endpoints. Only point estimates by treatment group are provided for Tier 3 safety parameters.

Safety Tier	Safety Endpoint	95% CI for Treatment Comparison	Descriptive Statistics
Tier 2	Grade 3-5 AE (incidence ≥5% of participants in one of the treatment groups)	Х	Х
	Serious AE (incidence ≥1% of participants in one of the treatment groups)	Х	X
	AEs (incidence $\geq 10\%$ of participants in one of the treatment groups)	X	Х
Tier 3	Any AE		Х
	Any Grade 3-5 AE		Х
	Any Serious AE		Х
	Any Drug-Related AE		X
	Any Serious and Drug-Related AE		X
	Any Grade 3-5 and Drug-Related AE		X
	Discontinuation due to AE		X
	Death		X
	Specific AEs, SOCs (incidence <10% of participants in all of the treatment groups)		Х
	Change from Baseline Results (lab toxicity shift, vital signs)		X
Abbreviati	ons: AE=adverse event; CI=confidence interval; SOC=system or	rgan class.	

Table 14 Analysis Strategy for Safety Parameters

9.6.3 **Statistical Methods for Patient-Reported Outcome Analyses**

This section describes the planned analyses for the PRO endpoints.

Mean Change from Baseline

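### Should discontinuation due to an adverse event, a named secondary safety endpoint, have a between-arm confidence interval?

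*Combined protocol and SAP*

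**What the plan says.** The endpoint tables in Sections 1.1 and 3 list two endpoints under the secondary safety objective: adverse events, and "Study intervention discontinuations due to adverse events".

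Section 9.6.2 sorts safety results into tiers, and no Tier 1 events are expected. Tier 2 gets a Miettinen-Nurminen 95% interval for the difference in proportions. It covers AEs at 10% or more in a treatment group, Grade 3 to 5 AEs at 5% or more, and, in Table 14, "Serious AE (incidence ≥1% of participants in one of the treatment groups". Tier 3 gets estimates per arm only. For the last of the broad categories placed there, the text reads "discontinuation due to an AE will be considered Tier 3 endpoints. Only point estimates by treatment group are provided for Tier 3 safety parameters". The matching row of Table 14 carries no incidence condition. It is marked for descriptive statistics and not for a treatment-comparison interval.

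On the standing of the Tier 2 intervals, the section says that "the CIs should be regarded as a helpful descriptive measure to be used in safety review"; they are unadjusted and are not a formal method of judging significance.

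Amendment 04 dropped the final efficacy analysis but kept a safety analysis at the end of the study.

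**The concern.** Three things make this look wrong.

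First, an endpoint named in the objectives table gets less inferential support than individual AE terms that are named nowhere in advance.

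Second, the introduction to the tiers says "Other safety parameters will be considered Tier 2 or Tier 3 based on the observed proportions of participants with an event". On that sentence alone, a discontinuation rate above 10% ought to reach Tier 2, but the later list fixes it in Tier 3 whatever its rate.

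Third, the contrast with rare events is awkward. A serious AE term seen in a few people would be shown with its uncertainty, while a summary of tolerability that may involve far more people would appear as two bare percentages.

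If this were a real gap, the end-of-study safety report would understate or hide the imprecision of a tolerability comparison, and a chance imbalance could be taken for a real one.

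**Working it through.** The plan states no figure for this endpoint, so there is none to reproduce. The check has two parts: a reading of the rule, and the size of what is left out.

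**1. Is the rule contradictory or incomplete?** The sentence on observed proportions is general. The Tier 3 paragraph then assigns seven broad categories by name: any AE, drug-related AE, serious AE, serious and drug-related AE, Grade 3-5 AE, drug-related Grade 3-5 AE, and discontinuation due to an AE. Table 14 repeats all seven without thresholds and adds death. The specific list qualifies the general sentence, and text and table agree. An analyst knows exactly what to produce.

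**2. Is this endpoint treated differently from its peers?** No. Tier 2 covers individual events above a threshold; the overall totals sit in Tier 3. Setting a single serious AE term against the discontinuation total compares two levels of summary. Like is treated alike: the totals for serious AEs and Grade 3-5 AEs, and deaths, have no interval either.

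**3. Does the objective call for a comparison?** In the same table, the OS and PFS objectives are to compare, and those for response rate, response duration and patient-reported outcomes are worded as relative to the atezolizumab arm. The safety objective is to evaluate the investigational combination on the proportion of AEs. Per-arm proportions answer that.

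**4. How large is the omitted interval?** The documents give neither the size of the treated population nor any AE rate, so both are assumed here. Section 9.9 gives 450 randomized 1:1, so 450 / 2 = 225 per arm if all are treated; 200 per arm is a lower assumption.

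The Miettinen-Nurminen limits are the values of d at which

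z(d) = (p1 − p2 − d) / √V(d) = ±1.96, with V(d) = [r1(1 − r1)/n1 + r2(1 − r2)/n2] × N/(N − 1),

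where p1 and p2 are the observed proportions, r1 and r2 are their maximum likelihood estimates under r1 − r2 = d, and N = n1 + n2.

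Entry to Tier 2 for a serious AE term: 1% × 225 = 2.25, so 3 participants; 1% × 200 = 2.

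| Assumed counts | Per arm | Difference, points | 95% interval | In the planned table? |
|---|---|---|---|---|
| Serious AE term, 3 vs 0 | 225 | 1.3 | −0.4 to 3.9 | yes |
| Serious AE term, 2 vs 0 | 200 | 1.0 | −0.9 to 3.6 | yes |
| Discontinuation, 23 vs 23 | 225 | 0 | −5.7 to 5.7 | no |
| Discontinuation, 45 vs 45 | 225 | 0 | −7.4 to 7.4 | no |
| Discontinuation, 68 vs 68 | 225 | 0 | −8.5 to 8.5 | no |
| Discontinuation, 34 vs 23 | 225 | 4.9 | −1.3 to 11.2 | no |
| Discontinuation, 45 vs 23 | 225 | 9.8 | 3.2 to 16.5 | no |
| Discontinuation, 30 vs 20 | 200 | 5.0 | −1.5 to 11.7 | no |
| Discontinuation, 40 vs 20 | 200 | 10.0 | 3.1 to 17.1 | no |

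Each row needs only two counts and two denominators. The interval is therefore recoverable from the planned output.

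**5. Would a change to Section 9.6.2 improve the evidence now?** Section 9 sends changes to nonconfirmatory analyses to the supplemental SAP if they are made before any analysis is conducted. The interim efficacy and safety analysis (cutoff 04-JUN-2024) is done and the study is unblinded, so an amendment could no longer make the interval prespecified. The route that remains is already in the plan: "Post hoc exploratory analyses will be clearly identified in the CSR".

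**The case for a change.** The strongest case for the addition comes from the plan's own reasoning. It defends the 10% threshold on the ground that rarer events contribute little to judging treatment differences, and it calls the intervals helpful for safety review. A named endpoint that may well exceed 10% fits that reasoning better than a serious AE term at 1%. The method is already specified, one extra interval costs almost nothing, and the end-of-study safety analysis is still to come. In the table above, 34 vs 23 is compatible with no difference and 45 vs 23 is not, yet the planned output would show only percentages for both.

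The facts in this stand, and the interval would be convenient. It does not follow that the plan is deficient. Sorting these cases by whether the interval includes zero is close to the significance reading that Section 9.6.2 rules out. An interval for this one total would also make the scheme less uniform.

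A further argument concerns the switch after the interim analysis, when "all ongoing participants on MK-7684A treatment will be offered the option to move to the comparator arm". Section 9.5.2 assigns people for safety as follows: "This will be the treatment group to which they are randomized except for participants who take incorrect study intervention for the entire treatment period". Switched participants therefore stay in Arm A, and Sections 9.5.2 and 9.6.2 give no rule for their later events. That is a separate question touching every safety table, and it does not show that this endpoint needs an interval. It also weakens the case for one: stopping MK-7684A early cut short Arm A's time at risk, so a crude difference in proportions would be harder to interpret.

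**Conclusion.** The concern does not hold. The plan states a clear, internally consistent convention, applies it to every broad AE category and to death, and meets a safety objective that is descriptive and carries no hypothesis. What is left out is a descriptive interval with a half-width of roughly 6 to 9 points for equal rates of 10% to 30%. That size rests on assumed rates and an assumed 200 to 225 treated per arm; nothing in the documents points to a treated population as small as 200. The reading of the plan does not depend on those assumptions. No result, error rate or decision would change, readers can calculate the interval from the reported counts, and the sponsor may report it as a labelled post hoc analysis without amending the SAP. Whether to show it is a matter of preference.

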9.6.4 Summaries of Baseline Characteristics and Demographics

The comparability of the treatment groups for each relevant characteristic will be assessed using tables and/or graphs. No statistical hypothesis tests will be performed on these characteristics. The number and percentage of participants randomized and the primary reason for discontinuation will be displayed. Demographic variables (such as age), baseline characteristics, and prior and concomitant therapies will be summarized by treatment either by descriptive statistics or categorical tables.

9.7 Interim Analyses

Protocol Amendment 04 implementation: the prespecified final analysis of the study described in the SAP will not be performed. Safety analysis will be performed at the end of the study. The subsections below are retained for reference.

The eDMC will serve as the primary reviewer of the results of the IA (analyses) and will make recommendations for discontinuation of the study or modification to the executive oversight committee of the Sponsor. If the eDMC recommends modifications to the design of

the protocol or discontinuation of the study, this executive oversight committee and potentially other limited Sponsor personnel may be unblinded to the treatment level in order to act on these recommendations. The extent to which individuals are unblinded with respect to results of interim analyses will be documented by the unblinded study team. Additional logistic details will be provided in the eDMC Charter.

Treatment-level results of the IA will be provided by the unblinded statistician to the eDMC. Prior to final study unblinding, the unblinded statistician will not be involved in any discussions regarding modifications to the protocol or statistical methods, identification of protocol deviations, or data validation efforts after the interim analyses.

9.7.1 Efficacy Interim Analyses

Table 16Summary of Interim and Final Analyses Strategy

CCI			

9.7.2 Safety Interim Analyses

9.8 Multiplicity

The study strictly controls t	type I error at 0.025 1-sided ^{CCI}
CCI	
Figure 4	Multiplicity Diagram for Type I Error Control

9.8.1 Overall Survival

CCI	9	1	5	

Table 17Efficacy Boundaries and Properties for OS Analyses

9.8.2 Progression-free Survival

 Table 18
 Efficacy Boundaries and Properties for PFS Analysis

CCI		

9.8.3 Safety Analyses

The eDMC has responsibility for assessment of overall risk/benefit. When prompted by safety concerns, the eDMC can request corresponding efficacy data. eDMC review of efficacy data to assess the overall risk/benefit to study participants will not require a

multiplicity adjustment typically associated with a planned efficacy IA.

9.9 Sample Size and Power Calculations

The study will randomize approximately 450 subjects in a 1:1 ratio into the experimental arm of MK-7684A in combination with etoposide/platinum and the control arm of atezolizumab in combination with etoposide/platinum. OS is primary endpoint for the study, with PFS as the secondary endpoint.

9.10 Subgroup Analyses

To determine whether the treatment effect is consistent across various subgroups, the between-group treatment effect for OS, PFS and ORR (with a nominal 95% CI) will be estimated and plotted within each category

The subgroup analyses for PFS and OS will be conducted using an unstratified Cox model, and the subgroup analyses for ORR will be conducted using the unstratified M&N method.

9.11 Compliance (Medication Adherence)

Drug accountability data for study treatment will be collected during the study. Any deviation from protocol-directed administration will be reported.

9.12 Extent of Exposure

Extent of exposure for a participant is defined as the number of cycles in which the participant receives the study medication infusion (see Section 8.6). Summary statistics will be provided on the extent of exposure for the APaT population.

10 SUPPORTING DOCUMENTATION AND OPERATIONAL CONSIDERATIONS

10.1 Appendix 1: Regulatory, Ethical, and Study Oversight Considerations

10.1.1 Code of Conduct for Interventional Clinical Trials

Merck Sharp & Dohme LLC, Rahway, NJ, USA (MSD)

Code of Conduct for Interventional Clinical Trials

I. Introduction

A. Purpose

MSD, through its subsidiaries, conducts clinical trials worldwide to evaluate the safety and effectiveness of our products. As such, we are committed to designing, implementing, conducting, analyzing, and reporting these trials in compliance with the highest ethical and scientific standards. Protection of participants in clinical trials is the overriding concern in the design and conduct of clinical trials. In all cases, MSD clinical trials will be conducted in compliance with local and/or national regulations (including all applicable data protection laws and regulations), Regulation (EU) 536/2014, and International Council for Harmonisation Good Clinical Practice (ICH-GCP), and also in accordance with the ethical principles that have their origin in the Declaration of Helsinki.

B. Scope

Highest ethical and scientific standards shall be endorsed for all clinical interventional investigations sponsored by MSD irrespective of the party (parties) employed for their execution (e.g., contract research organizations, collaborative research efforts). This Code is not intended to apply to trials that are observational in nature, or which are retrospective. Further, this Code does not apply to investigator-initiated trials, which are not under the full control of MSD.

II. Scientific Issues

A. Trial Conduct

1. Trial Design

Except for pilot or estimation trials, clinical trial protocols will be hypothesisdriven to assess safety, efficacy and/or pharmacokinetic or pharmacodynamic indices of MSD or comparator products. Alternatively, MSD may conduct outcomes research trials, trials to assess or validate various endpoint measures, or trials to determine patient preferences, etc.

The design (i.e., participant population, duration, statistical power) must be adequate to address the specific purpose of the trial and shall respect the data protection rights of all participants, trial site staff and, where applicable, third

parties. All trial protocols are and will be assessed for the need and capability to enroll underrepresented groups. Participants must meet protocol entry criteria to be enrolled in the trial.

2. Site Selection

MSD's clinical trials are conducted globally in many different countries and in diverse populations, including people of varying age, race, ethnicity, gender, and accounting for other potential disease related factors. MSD selects investigative sites based on medical expertise, access to appropriate participants, adequacy of facilities and staff, previous performance in clinical trials, as well as budgetary considerations. Prior to trial initiation, sites are evaluated by MSD personnel (or individuals acting on behalf of MSD) to assess the ability to successfully conduct the trial.

Where appropriate, and in accordance with regulatory authority guidance, MSD will make concerted efforts to raise awareness of clinical trial opportunities in various communities. MSD will seek to engage underrepresented groups and those disproportionately impacted by the disease under study. MSD will support clinical trial investigators to enroll underrepresented groups and expand access to those who will ultimately use the products under investigation.

3. Site Monitoring/Scientific Integrity

Investigative trial sites are monitored to assess compliance with the trial protocol and Good Clinical Practice (GCP). MSD reviews clinical data for accuracy, completeness, and consistency. Data are verified versus source documentation according to standard operating procedures. Per MSD policies and procedures, if potential fraud, scientific/research misconduct, privacy incidents/breaches or Clinical Trial-related Significant Quality Issues are reported, such matters are investigated. When necessary, appropriate corrective and/or preventative actions are defined and regulatory authorities and/or ethics review committees are notified.

B. Publication and Authorship

Regardless of trial outcome, MSD commits to publish the primary and secondary results of its registered trials of marketed products in which treatment is assigned, according to the pre-specified plans for data analysis. To the extent scientifically appropriate, MSD seeks to publish the results of other analyses it conducts that are important to patients, physicians, and payers. Some early phase or pilot trials are intended to be hypothesis-generating rather than hypothesis testing; in such cases, publication of results may not be appropriate since the trial may be underpowered and the analyses complicated by statistical issues such as multiplicity.

MSD's policy on authorship is consistent with the recommendations published by the International Committee of Medical Journal Editors (ICMJE). In summary, authorship should reflect significant contribution to the design and conduct of the

trial, performance or interpretation of the analysis, and/or writing of the manuscript. All named authors must be able to defend the trial results and conclusions. MSD funding of a trial will be acknowledged in publications.

III. Participant Protection

A. Regulatory Authority and Ethics Committee Review (Institutional Review Board [IRB]/Independent Ethics Committee [IEC])

All protocols and protocol amendments will be submitted by MSD for regulatory authority acceptance/authorization prior to implementation of the trial or amendment, in compliance with local and/or national regulations.

The protocol, protocol amendment(s), informed consent form, investigator's brochure, and other relevant trial documents must be reviewed and approved by an IRB/IEC before being implemented at each site, in compliance with local and/or national regulations. Changes to the protocol that are required urgently to eliminate an immediate hazard and to protect participant safety may be enacted in anticipation of ethics committee approval. MSD will inform regulatory authorities of such new measures to protect participant safety, in compliance with local and/or national regulations.

B. Safety

The guiding principle in decision-making in clinical trials is that participant welfare is of primary importance. Potential participants will be informed of the risks and benefits of, as well as alternatives to, trial participation. At a minimum, trial designs will take into account the local standard of care.

All participation in MSD clinical trials is voluntary. Participants enter the trial only after informed consent is obtained. Participants may withdraw from an MSD trial at any time, without any influence on their access to, or receipt of, medical care that may otherwise be available to them.

C. Confidentiality

MSD is committed to safeguarding participant confidentiality, to the greatest extent possible, as well as all applicable data protection rights. Unless required by law, only the investigator, Sponsor (or individuals acting on behalf of MSD), ethics committee, and/or regulatory authorities will have access to confidential medical records that might identify the participant by name.

D. Genomic Research

Genomic research will only be conducted in accordance with a protocol and informed consent authorized by an ethics committee.

IV. Financial Considerations

A. Payments to Investigators

Clinical trials are time- and labor-intensive. It is MSD's policy to compensate investigators (or the sponsoring institution) in a fair manner for the work performed in support of MSD trials. MSD does not pay incentives to enroll participants in its trials. However, when enrollment is particularly challenging, additional payments may be made to compensate for the time spent in extra recruiting efforts.

MSD does not pay for participant referrals. However, MSD may compensate referring physicians for time spent on chart review and medical evaluation to identify potentially eligible participants.

B. Clinical Research Funding

Informed consent forms will disclose that the trial is sponsored by MSD, and that the investigator or sponsoring institution is being paid or provided a grant for performing the trial. However, the local ethics committee may wish to alter the wording of the disclosure statement to be consistent with financial practices at that institution. As noted above, all publications resulting from MSD trials will indicate MSD as a source of funding.

C. Funding for Travel and Other Requests

Funding of travel by investigators and support staff (e.g., to scientific meetings, investigator meetings, etc.) will be consistent with local guidelines and practices.

V. Investigator Commitment

Investigators will be expected to review MSD's Code of Conduct as an appendix to the trial protocol, and in signing the protocol, agree to support these ethical and scientific standards.

